7.2 ANALYSIS SETS

Total Set: The total set consists of all subjects who signed the informed consent form, including subjects withdrawn prior to randomization.

Full Analysis Set (FAS): This will consist of all subjects randomized to receive study treatment whether or not they received treatment. Subjects will be reported according to their randomized treatment group regardless of treatment received.

Per-Protocol Analysis Set (PPS): The PPS will consist of subjects in the FAS with the additional following criteria for exclusion:

- Did not receive study treatment as per randomization schedule (including not receiving any randomized treatment)
- Dose of randomized treatment was adjusted.

CROSS-REGIONAL TEMPLATE

Template Number: C-TMPL-DO-801

Page: 11 of 28

Version Number: 1.2

Effective Date: 14 Sep 2015

This version replaces: 1.1

Parent Document: C-SOP-DO-800

Template Title: Statistical Analysis Plan (Legacy Takeda)

- Violated inclusion criteria, such as:
 - Does not have a history of constipation defined as SBM frequency of less than 3 times per week on average for 6 months or longer (and observed during Screening Period).
 - Does not have SBMs with ≥ 1 of the following 3 symptoms for the last 6 months or longer, in at least 1 out of every 4 bowel movements: scybalum stool or hard feces, straining, or the sensation of incomplete evacuation.
 - The subject rarely has loose stools without the use of laxatives.
- Violated exclusion criteria, such as:
 - The subject has a history or clinical manifestations of significant mechanical obstruction (intestinal obstruction due to tumor, hernia etc).
 - Has chronic constipation due to a secondary cause (medications, diabetes mellitus, hypothyroidism, depression, etc).
 - Has sufficient criteria for IBS or there is a functional defecation disorder.
 - BM frequency is 3 or more per week.
 - SBM frequency has been less than 3 times per week for less than 6 months in duration or whose symptoms associated with SBM have been present for less than 6 months (hard feces, sensation of incomplete evacuation, or straining).
 - Received treatment with a rescue medication within 24 hours prior to the first dose on the morning of Day 1.
 - Has megacolon/megarectum or has received a diagnosis of intestinal pseudo-obstruction.
 - Has confirmed or suspected organic disorders of the large intestine (obstruction, stenosis, carcinoma, or inflammatory bowel disease). Any subject in whom total colonoscopy has detected a polyp requiring treatment is excluded from this study.
 - Has been hospitalized for gastrointestinal or abdominal surgery within 3 months before the start of this study.
 - Use of any excluded medications, procedures or treatments prior to the assessment of the primary endpoint.

Any other significant event interfering with efficacy evaluation of primary endpoint, to be decided at a Targeted Data Review Meeting. Definitions of criteria constituting major deviations will be provided, prior to unblinding.

CROSS-REGIONAL TEMPLATE

Template Number: C-TMPL-DO-801

Page: 12 of 28

Version Number: 1.2

Effective Date: 14 Sep 2015

This version replaces: 1.1

Parent Document: C-SOP-DO-800

Template Title: Statistical Analysis Plan (Legacy Takeda)

Subjects will be reported in according to their treatment group. Since subjects not receiving treatment per the randomization schedule are excluded from the PPS, this will be their actual treatment.

Safety Analysis Set (SAF): This will consist of all subjects who receive study treatment. Subjects will be assigned to the treatment group according to the actual treatment received.

The FAS will be used for efficacy analyses. Supportive analyses based on the PP will be performed for the primary efficacy variable. The SAF will be used for all safety analyses.

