For BM data the assignment of data to each week (1, 2, 3 and 4) will be calculated from the date and time of the morning dose on Day 1. If no morning dose was taken on Day 1, then the date of Day 1 will be used and the time of the first recorded morning dose will be used. Weeks will be calculated as 168-hour intervals starting from this time. Note that any diary entries prior to this will be assigned to the screening period. Where missing dates or times do not allow the assignment of diary data to a treatment period (Screening or double blind) then it will be assumed that all data in the Screening booklet was recorded during Screening and all data in the remaining booklets were recorded after the booklets were provided to subjects. Abdominal symptom assessments will be assigned to the week as recorded in the diary. PAC-QOL is assessed at Day -1, Week 2 (Day 15) and Week 4 (Day 29). PAC-QOL assessments will be assigned to the time point relating to the visit at which they are recorded, regardless of actual study day. Assessments conducted at an Early Termination Visit will be assigned to the next scheduled visit that would have taken place if the subject had not discontinued, e.g. if the subject withdraws prior to Week 2 then the Early Termination Visit assessment will map to Week 2, whereas if the Early Termination Visit occurs after Week 2 then the assessment will be assigned to Week 4. Study visits are presented in the table below.

Study Day/Week	Screening		Double Blind Treatment Period				Follow-up Phone Contact
	Screening	Randomization	First Dose	Week 1	Week 2	Final Visit / Early Termination Visit Week 4	
Visit Number:	1	2	-	3	4	5	-
Day	-15	-1	1	8	15	29	43

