7.8.1 Primary Efficacy Endpoint(s)

The primary efficacy endpoint is SBM frequency at Week 1; an SBM is defined as any BM that does not occur within 24 hours after rescue medication use. Since rescue medication use will be disallowed during Week 1, the SBM frequency should equal the BM frequency. In the case of protocol violators, the analysis will be based on SBMs.

In order to adjust for early withdrawals or those with less than 7 days diary data, weekly SBM frequency will be calculated as follows:

$$7 \times (\text{Number of SBMs} / \text{Number of days}),$$

where the number of days is the number of days during the week that the subject was in the study. Weeks will be calculated as 168-hour intervals starting from the day after randomization (Day1), if there is no time recorded for the morning dose on Day1 then the time of the first recorded morning dose will be used. The number of days will generally be 7 unless a subject drops out during a treatment week. If the number of days is less than 4, then the data will be considered insufficient and the frequency will be missing.

Primary Analysis

Since outliers are commonly observed in these data, parametric models may not be robust. The efficacy data will therefore be analyzed by a van Elteren test stratified by center. If necessary, small centers will be pooled as mentioned above. This procedure will test the null hypothesis of equal SBM rates between treatments at the end of Week 1 versus the alternative hypothesis of non-equality between the 2 groups; the test will be conducted at a 2-sided significance level of 0.05. A related 95% confidence interval and point estimate will be provided for the treatment difference; the confidence interval will be estimated by inverting the hypothesis test. This endpoint will be analyzed for the FAS.

Sensitivity Analyses

The primary analysis as described above will be repeated using the PP rather than the FAS. An additional sensitivity analysis using the FAS assuming a ‘worse-case’ scenario approach will also be conducted, where missing values, including those with < 4 days diary data, are assigned the worst case values (the lowest SBM frequency for week 1) recorded in the study by any subject for that endpoint at that time.

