Additionally the endpoint will be analyzed using robust analysis of variance (ANOVA) models (by M-estimation [3] using PROC ROBUSTREG in SAS) with center and treatment in the model as a sensitivity analysis using the FAS. The interaction between treatment and center will also be examined in a separate model, using robust ANOVA methods as previously described.

To examine the effects of any permanent dose reduction in response to an AE (as recorded on the eCRF) an additional sensitivity analysis will also be performed. This will be performed on the FAS where data from those subjects with a dose reduction will be excluded from the time of dose reduction (taken as date of last BID dose + 12 hours, e.g. if the evening dose is removed

CROSS-REGIONAL TEMPLATE

Template Number: C-TMPL-DO-801

Page: 19 of 28

Version Number: 1.2

Effective Date: 14 Sep 2015

This version replaces: 1.1

Parent Document: C-SOP-DO-800

Template Title: Statistical Analysis Plan (Legacy Takeda)

then the time will be from the morning dose + 12 hours, if the morning dose is removed then it will be from the previous day's evening dose + 12 hours) and subjects will be treated as a drop-out from this time point onwards. This will be implemented using robust ANOVA. Additionally, another factor will be added to the robust ANOVA model to examine the effect of dose reduction. This will be performed on the FAS. This analysis will not be carried out if the number of subjects with a dose reduction within the first week is less than 5%.

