7.8.2 Secondary Efficacy Endpoint(s)

The interaction of treatment and center and the effect of dose reduction will not be examined for any secondary endpoints. All secondary endpoints will be analyzed for the FAS only.

SBM frequency at Week 2, 3 and 4

The secondary endpoint will be analyzed as specified for the primary endpoint separately for each week.

Additionally for patients with a missing Week 2 frequency estimate (where diary days < 4 in Week 2) the Week 1 estimate will be carried forward, if available. For the worse-case analysis all missing Week 2 values will be assigned the lowest SBM frequency for week 2.

Proportion of subjects with an SBM within 24 hours after first dose

The 24 hour period will be taken from the time of the first recorded dose in the patient diary. If the efficacy data is missing for the first 24 hours following this dose then it will be assumed that the patient did not experience any BM (including SBMs) during this period, this is based on the assumption that a patient is more likely to complete the diary on any particular day if they experience a BM than if they did not. The proportion of subjects with an SBM within 24 hours after first dose in Week 1 will be analyzed by a Cochran-Mantel-Haenszel (CMH) test stratified by center. Additionally a logistic regression model will be used with treatment and center as factors as a sensitivity analysis. The estimated odds ratio and associated 95% CI for both methods will be presented to aid interpretation of the clinical effect.

Mean Degree of Straining (Week 1, 2, 3, and 4)

For each BM patients should indicate the degree of straining associated with that BM. The degree of straining is a 5 point scale:

0 = No straining

1 = Mild straining

2 = Moderate straining

3 = Strong straining

4 = Very strong straining

CROSS-REGIONAL TEMPLATE

Template Number: C-TMPL-DO-801

Page: 20 of 28

Version Number: 1.2

Effective Date: 14 Sep 2015

This version replaces: 1.1

Parent Document: C-SOP-DO-800

Template Title: Statistical Analysis Plan (Legacy Takeda)

For each subject, the mean degree of straining will be averaged for all SBMs in a given week. The mean degree of straining will then be analyzed by van Elteren tests, stratified by center, at Weeks 1, 2, 3, and 4 separately. A related 95% confidence interval and point estimate will be provided for the treatment difference; the confidence interval will be estimated by inverting the hypothesis test.

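### The per-protocol set drops every dose-adjusted subject with no time limit, although it is used only for the Week 1 endpoint

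*SAP*

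**What the plan says.** SAP 7.2 builds the PPS from the FAS by a list of exclusions. One reads "Dose of randomized treatment was adjusted", with no reference to when.

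The PPS has a single use. SAP 7.2 states "Supportive analyses based on the PP will be performed for the primary efficacy variable", and SAP 7.8.1 carries this out: "The primary analysis as described above will be repeated using the PP rather than the FAS". For later weeks SAP 7.8.2 says "All secondary endpoints will be analyzed for the FAS only". The primary variable is SBM frequency in Week 1. SAP 7.1 anchors the weeks at the Day 1 morning dose: "Weeks will be calculated as 168-hour intervals starting from this time".

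The row for optional dose reduction in Protocol Appendix A is marked at Visit 3 (Day 8) and Visit 4 (Day 15). Protocol 9.3 allows 2 days either side of a visit, and Protocol 7.7 allows a reduction between visits after an adverse event report.

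Another PPS exclusion in the same list does carry a time limit: "Use of any excluded medications, procedures or treatments prior to the assessment of the primary endpoint".

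**The concern.** A per-protocol set should remove subjects whose departure from the protocol could have affected the endpoint being analysed. A dose reduction in Week 2, 3 or 4 cannot change what was recorded in Week 1. As written, the criterion still removes that subject from the only analysis the PPS supports.

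Excluding on an event that follows the outcome costs usable data at the least. If the later reduction is associated with Week 1 bowel response, it also moves the PPS estimate away from the FAS estimate for a reason that has nothing to do with Week 1 adherence. A reader comparing the two could misread the gap. The documents leave that association open. The design text (Protocol 6.1, SAP 4.2) lets adjustment take bowel movement frequency and consistency into account, while Protocol 7.7 and Appendix A note (n) tie it to adverse events. Those passages need to be reconciled with each other.

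**Working it through.** The plan gives no figure for PPS losses, so there is none to reproduce. The check covers timing first and size second.

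**Timing.** Take the Day 1 morning dose as 0 h; Week 1 then closes at 168 h. SAP 7.8.1 dates a reduction as "taken as date of last BID dose + 12 hours". If doses are exactly 12 h apart (an assumption), a reduction agreed on Day d is dated as follows:

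- that morning's capsule is the first omitted: 24(d−1)
- that evening's capsule: 24(d−1) + 12
- the next morning's capsule: 24d

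| Visit day | Dated at (h) |
|---|---|
| Day 6 (early Visit 3) | 120, 132, 144 |
| Day 7 (early Visit 3) | 144, 156, 168 |
| Day 8 (nominal Visit 3) | 168, 180, 192 |
| Day 15 (nominal Visit 4) | 336, 348, 360 |

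On these terms the nominal visits fall at or after the close of Week 1. An early Visit 3 or an unscheduled report can fall inside it.

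The 12-hour spacing matters at the boundary, because doses go with breakfast and dinner. With assumed times of 08:00 and 19:00, the Day 7 evening dose is at 6 × 24 + 11 = 155 h. Omitting the Day 8 morning capsule is then dated 155 + 12 = 167 h, just inside Week 1, although no Day 1 to Day 7 capsule was omitted.

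**Size if reduction is unrelated to Week 1 SBM.** Let a be the share of lubiprostone subjects first reduced after Week 1. Values of 5%, 10% and 15% are assumptions. With 102 per arm, none lost on placebo and equal SDs, the standard error is multiplied by √[(1 + 1/(1−a))/2].

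| a | Lost of 102 | SE ratio |
|---|---|---|
| 5% | about 5 | 1.013 |
| 10% | about 10 | 1.027 |
| 15% | about 15 | 1.043 |

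There is no bias in this case.

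**Size if it is related.** Protocol Table 4.a gives, for SC0232 at Week 1, 5.89 (SD 4.02) on lubiprostone and 3.99 on placebo, a difference of 5.89 − 3.99 = 1.90. Take a = 10%, on lubiprostone only.

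1. *Exclusion probability proportional to SBM.* The retained mean falls by a·SD²/[mean·(1−a)] = 0.10 × 4.02²/(5.89 × 0.90) = 0.305. The difference becomes 1.90 − 0.305 = 1.60.
2. *The highest 10% removed.* Negative binomial draws matched to 5.89 and 4.02 (size 5.89²/(4.02² − 5.89) = 3.38) give a retained mean of about 4.95. The difference is 4.95 − 3.99 = 0.96.
3. *Low-SBM subjects favoured for exclusion*, with weight 1/(1 + SBM) scaled to 10%. The same draws give a retained mean of about 6.15, a difference of 6.15 − 3.99 = 2.16.

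These are differences in means. The PPS analysis itself is a van Elteren test with a test-inverted interval, so they indicate direction and scale only.

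**The case against.** The strongest reply is that excluding anyone who left the assigned regimen is a common strict per-protocol definition, and that the analysis is only supportive. The second half stands: the FAS primary test keeps every later-reduced subject, and alpha and sample size do not change. The first half does not rescue the criterion, because no planned PPS analysis uses data after Week 1.

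It is also fair that nothing schedules a reduction. The Appendix A row is optional, reductions may occur between visits, and neither rate nor timing is given. The number of subjects wrongly removed could be zero.

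Nor is the excluded-medication criterion proof of a general rule: the exclusion for treatment not received as randomized has no time limit either. The comparison shows only that the plan can write such a limit where it matters.

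Some of the visibility is already in place. SAP 7.3 presents reasons for exclusion, and Protocol 13.1.1 has them documented and signed before database lock. SAP 7.3 does not say that PPS exclusion reasons are shown by arm. The open clause, "Any other significant event interfering with efficacy evaluation of primary endpoint", adds exclusions and cannot narrow this one. The major-deviation definitions are still to come, so a limit could yet be set, but the current text has none.

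Three stronger readings are tempting, and the documents do not support them:

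- *The bias must run toward the null.* That follows only if reducers have high Week 1 SBM. Case 3 runs the other way.
- *1.60 is a worst case.* Case 2 is lower, and none of the three is a bound.
- *The dose-reduction analyses in SAP 7.8.1 disappear when fewer than 5% reduce in Week 1.* The sentence is singular and follows the model with the added dose-reduction factor, so it may switch off that model alone. Protocol 13.1.3.1 plans both analyses with no such trigger. The truncation analysis, if run, keeps all Week 1 data of later reducers.

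**Conclusion.** The point holds, and it is minor. The criterion in SAP 7.2 is wider than the use of the PPS justifies: it discards Week 1 data because of an event after Week 1. It is not empty, since reductions inside Week 1 are possible.

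The effect is confined to one supportive analysis. If reduction is unrelated to Week 1 SBM, the cost is a standard error about 1% to 4% larger over the assumed 5% to 15% range. If it is related, the size and direction are unknown. The illustrations at 10% run from a difference about 49% smaller (0.94/1.90) to about 14% larger (0.26/1.90). They rest on SC0232 moments, an assumed rate, reductions on lubiprostone only and, for cases 2 and 3, a negative binomial shape.

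**What to change.** In SAP 7.2, limit the dose-adjustment exclusion to adjustments made before the end of Week 1. Define this as the first capsule omitted because of the adjustment having been due on Day 1 to Day 7. Counting by the omitted capsule avoids the boundary error that the 12-hour dating rule produces when doses are not exactly 12 h apart. Apply the limit to any adjustment, whatever its recorded reason.

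In SAP 7.3, present PPS exclusion reasons by treatment arm.

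An exclusion for a reduction inside Week 1 may still be related to response, so the PPS should stay supportive and be read beside the FAS.

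The cost is one criterion and one table split, both settled before unblinding. The PPS would no longer reflect full-course dosing, which no planned PPS analysis uses. No dosing rule changes.

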Approximately 204 subjects whose constipation is confirmed during the Screening Period will be randomized in the Double-Blind Treatment Period to receive either lubiprostone or matching placebo BID. Others whose constipation does not satisfy the criteria during the 14-day Screening Period or those who receive a rescue medication within 24 hours prior to the first dose on Day 1 are ineligible for randomization in the Double-Blind Treatment Period and therefore will be excluded from the study. Subjects who satisfy the inclusion criteria and do not meet the exclusion criteria are randomized to 1 of the treatment groups in the order of the number assigned. Approximately 204 subjects with CIC will be randomized to 2 groups: active treatment or placebo in a 1:1 ratio (102 subjects each) in a double-blinded manner.

[figure not shown]
Subjects are to begin their study drug treatment twice daily (after breakfast and dinner) in the morning following Visit 2.

Subjects will return to the study site on approximately Study Days 8, 15, and 29 during the 4 weeks of double-blind treatment and will be followed for an additional 2 weeks during the Follow-Up Period, in which no treatment will be administered.

At the investigator's discretion, with consideration to subject's bowel movement frequency and consistency, dose adjustments (dose reduction) may be made in a double-blind manner. Dose adjustment should be documented in the subject's source notes. Procedure for reduction of study drug dose due to Adverse Events is described in Section [7.7](#).

Subjects who withdraw prematurely will be seen within 1 week of discontinuation for an Early Termination Visit. A schematic of the study design is included as [Figure 6.a](#). A schedule of assessments is listed in [Appendix A](#).

Figure 6.a Schematic of Study Design

Note: Randomization occurs on Day -1 of the Screening Period. The first dose of study drug is administered the next day, on Day 1 of the Double-Blind Treatment Period.

Note: There is no treatment during the Follow-up Period.

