9.3.2 Study Entrance/Randomization

Randomization will take place on Day -1. The following procedures will be performed and documented during Randomization:

- Review diary entries for completeness and compliance. Evaluate the need for providing phone reminders to subjects who are not consistent or thorough with study diary completion.
- Check the use of rescue medication (by diary).
- Measurement of vital signs.
- Record use of concomitant medications.
- Urine hCG pregnancy test (for females of childbearing potential only).
- Abdominal symptom assessment review (by diary).
- Pretreatment Adverse Events assessment.
- PAC-QOL Questionnaire.
- Eligibility assessment (review Inclusion/ Exclusion criteria).
- Access IVRS/IWRS for Randomization and MED ID.

- Dispensing of study medication via IVRS/IWRS.
- Dispense study diary. Re-instruct subject on diary completion.
- Distribute rescue medications prescription as necessary.
- Schedule next visit 7 days from first dose of study medication.
- Instruct subject to bring the study medication bottle and the completed diary at Visit 3.
- Guidance on the avoidance of pregnancy and ova donation.

No rescue medication may be used within 24 hours before and 48 hours after the first dose of the study drug (Day 1). Subjects who use a rescue medication within 24 hours before the first dose of study drug on Day 1 should be withdrawn from the study. Those who use a rescue medication within 48 hours after dosing on Day 1 will be discontinued from the study by the investigator. The dose and mode of administration of rescue medications must be recorded in the electronic case report form (eCRF).

If the subject has satisfied all of the inclusion criteria and none of the exclusion criteria for randomization, the subject should be randomized using the IVRS/IWRS as described in Section 9.3.2. Subjects will be instructed to start study medication the following day (Day 1) as described in Section 6.1. Subjects will be instructed to take 1 capsule twice a day, orally, at the same time of day, preferably in the morning with breakfast and in the evening with dinner. The procedure for documenting Screening failures is provided in Section 9.1.15.

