Appendix A Schedule of Study Procedures

Study Day/Week	Screening	Randomization	Treatment			Follow-up Period	
	Day -15	Day -1 (a)	First Dose	Week 1	Week 2	Final Visit or Early Termination Visit Week 4 (c)	Follow-up Phone Contact Week 6 (o)
Visit Windows (Days):	-15 to -1	-1	1	8	15	29	43
Visit Number:	1	2	N/A	3	4	5	N/A
Informed consent	X						
Demographics and medical history (d)	X						
Inclusion/exclusion criteria (e)	X	X					
Medication history	X						
Physical examination	X					X	
Vital signs (f)	X	X				X	
Weight and height (g)	X					X	
Concomitant medications	X	X	X	X	X	X	X
Concurrent medical conditions	X						
Clinical laboratory tests (h)	X					X	
Pregnancy test (i)	X	X				X	
Urine drug screen	X						
Access IVRS/IWRS for Subject ID/MED ID/Subject Status	X	X				X	
Dispense investigational drug		X					
Distribute rescue medications prescription, as necessary	X	X		X	X		
Drug return/accountability/compliance				X	X		X
Distribution diaries to subjects	X	X		X	X		
Efficacy:							
Abdominal symptom assessment review (by diary)		X		X	X	X	
PAC-QOL		X			X	X	
Use of rescue medication (by diary)		X		X	X	X	
Diary-keeping by subjects (j)	X	X	X	X	X	X	
Diary collection/ compliance check (k)		X		X	X	X	
Safety:							
Guidance on avoidance of pregnancy and ova donation	X	X		X	X	X	
Pretreatment adverse events (l)	X	X					
Adverse events (m)			X	X	X	X	X
Dose reduction (optional) (n)				X	X		
Phone interview							X

Footnotes are on last table page.

N/A= not applicable.

- (a) Subjects will be randomized on Day -1, the last day of the Screening Period. They will also receive their bottle of dispensed investigational study drug on Day -1, although they will be instructed to take the first dose the next day, on Day 1.
- (b) Day 1 is the first day of study drug administration. Subjects are to take 1 capsule of lubiprostone 24 µg or placebo in the morning with 240 mL of water in the morning with breakfast and again in the evening with dinner. Repeat this regimen for 4 weeks.
- (c) Conduct Final Visit procedures for subjects discontinued early per Section 7.6. Subjects who withdraw prematurely should return within 1 week of discontinuation for an Early Termination Visit.

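### The per-protocol set drops subjects whose dose was adjusted at any time, although it serves only the Week 1 endpoint

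*SAP*

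**What the plan says.** SAP 7.2 lists, among the PPS exclusions, that "Dose of randomized treatment was adjusted". No time is attached. (Protocol 13.1.1 words this criterion in the negative, an evident slip that the SAP corrects.) Another criterion in the same SAP list does carry a limit: "Use of any excluded medications, procedures or treatments prior to the assessment of the primary endpoint".

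The PPS has one use. SAP 7.2 states that "Supportive analyses based on the PP will be performed for the primary efficacy variable", SAP 7.8.1 that "The primary analysis as described above will be repeated using the PP rather than the FAS", and SAP 7.8.2 that "All secondary endpoints will be analyzed for the FAS only". The primary variable is SBM frequency over the first 168 hours of treatment.

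On the timing of reductions, Protocol Appendix A has an optional dose-reduction row marked at Day 8 (Visit 3) and Day 15 (Visit 4). For Visit 3, Protocol 9.3.2 says "Schedule next visit 7 days from first dose of study medication". Under Protocol 9.1.17 the diary is collected and reviewed at Day 8. Protocol 7.7 also allows reductions between visits.

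On the grounds, Protocol 6.1 says that, at the investigator's discretion and with consideration of "bowel movement frequency and consistency, dose adjustments (dose reduction) may be made in a double-blind manner"; SAP 4.2 repeats this. Protocol 7.7, Protocol 9.3.3 and Appendix A footnote (n) describe reductions for adverse events.

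**The concern.** A dose change after the first 168 hours cannot affect Week 1 SBM frequency, the only outcome for which the PPS is used. The rule nevertheless removes such a subject. If the later reduction was prompted by many or loose stools in Week 1, or by an adverse event that goes with them, membership of the analysis set depends on the outcome being analysed.

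In all three studies in Protocol Table 4.a the lubiprostone arm has both the higher mean and the larger SD at Week 1. Selection on high counts would then remove mainly lubiprostone subjects and move the PPS estimate toward no difference. A PPS result weaker than the FAS result could be read as a sign of fragility when it came from the exclusion rule.

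**Working it through.** **Text.** Side by side, the sections give four facts: no time limit on the criterion; a PPS used for Week 1 only; reductions marked at visits that nominally follow Week 1; and bowel response as one stated consideration. A subject reduced at a Visit 3 or Visit 4 held on schedule has a complete Week 1 on the assigned regimen and is still excluded. The Targeted Data Review Meeting may add exclusions. Nothing gives it power to waive a listed one.

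**The plan's own figure.** There is none for the PPS. The planned total of 198 can be checked from a difference of 1.9, SD 4, 90% power and two-sided 0.05. Per arm, 2 × [4 × (1.960 + 1.282)/1.9]² = 93.1. Multiplying by π/3 for the Wilcoxon test gives 97.5, so 98 per arm and 196 in total. A t-based version gives 200 and Noether's formula 202.5, so 198 is reproduced within 3%. It does not depend on the PPS rule.

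**Inputs for the size.** Week 1 mean ± SD from Protocol Table 4.a, placebo then lubiprostone: SC0232 3.99 ± 2.70 and 5.89 ± 4.02; SC0131 3.46 ± 2.28 and 5.69 ± 4.41; SC0831 2.93 ± 1.82 and 5.37 ± 2.78. Planning values: 4 and 5.9, SD 4 in both arms. The number reduced after Week 1, and its relation to the Week 1 count, are assumptions.

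**Moderate selection, by formula.** If the chance of reduction is proportional to the Week 1 count and a fraction f of an arm is removed, the retained mean is m − [f/(1 − f)] × s²/m, whatever the distribution. SC0232 values, with 5% of lubiprostone (5.1 of 102) and 1% of placebo (1.0 of 102) removed:
- Lubiprostone: 5.89 − (0.05/0.95) × (4.02²/5.89) = 5.89 − 0.0526 × 2.744 = 5.75.
- Placebo: 3.99 − (0.01/0.99) × (2.70²/3.99) = 3.99 − 0.0101 × 1.827 = 3.97.
- Difference: 5.75 − 3.97 = 1.78, against 5.89 − 3.99 = 1.90 with nobody removed.

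**Power, by simulation.** 102 per arm, 10 equal centers (assumed; the protocol plans about 10 sites), negative binomial counts matched to mean and SD, two-sided van Elteren test at 0.05, 2000 to 3000 trials per scenario. The starting power for SC0232 differs slightly between runs.

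| SC0232 values, assumed reductions after Week 1 | Power, all subjects → PPS |
|---|---|
| 3% in each arm, unrelated to response | 94.0% → 93.3% |
| Proportional to count, 3% v 1% | 94.6% → 92.4% |
| Proportional to count, about 5 v 1 subjects | about 93-94.5% → 90-91% |
| A quarter of those with ≥14 SBMs | 95.3% → 94.3% |
| Half of those with ≥14 SBMs | 94.0% → 90.9% |
| All with ≥14 SBMs (5.1 v 0.5 subjects) | 94.0% → 86.3% |
| All with ≥12 SBMs (9.5 v 1.4 subjects) | 94.0% → 77.3% |

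With all subjects at ≥14 SBMs removed, the mean difference falls from 1.9 to 1.4 and the Hodges-Lehmann difference from 1.5 to 1.3. The full comparison is significant and the PPS is not in 8% of trials.

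**Other inputs, same rule (all with ≥14 SBMs, both arms).** SC0131: 96.0% → 88.0%. SC0831: 100% throughout. Planning values: 98.5% → 98.6%, because an equal SD gives placebo a long upper tail too (5.0 v 3.3 subjects removed).

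The planning-value result depends on applying one rule to both arms. A separate Mann-Whitney simulation (99 per arm, planning values) assumed 5/10/15% of lubiprostone and 1/2/3% of placebo subjects reduced. PPS power went from about 98% to 97/96/93% with selection proportional to count. It went to 97/91/87% when the highest counts in each arm were removed.

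**The case against.** The main grounds described for reduction are adverse events, and an adverse event need not track the SBM count. If it does not, the estimate does not move and power changes only from 94.0% to 93.3%. Reductions are optional and not confined to the period after Week 1: they may be made between visits, the 2-day window in Protocol 9.3 can place Visit 3 before 168 hours, and SAP 7.8.1 foresees first-week reductions. Subjects reduced in Week 1 are properly excluded under any version of the rule.

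Safeguards also exist. SAP 7.3 reports the reason for exclusion from each set, so a gap between PPS and FAS would be traceable, and Protocol 13.1.1 fixes the sets before database lock. SAP 7.8.1 already plans a FAS analysis that drops data only from the time of reduction. A strict reading of per protocol as no dose change at all is a recognisable convention.

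These points limit the size. They do not supply a reason to remove a subject who was fully on regimen through the only period analysed. Reporting the reason for exclusion explains a distorted result but does not prevent it, and the SAP's own time limits elsewhere show the intended logic.

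A reader might infer that reductions are driven by bowel response, or that power will drop to 86%. The documents support neither: bowel response is one consideration beside the more detailed adverse-event procedure, and no section sets a threshold of 14 SBMs or any reduction rate.

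**Conclusion.** The rule is wrong as written, with minor consequences. It allows selection on a post-Week 1 event, possibly related to the outcome, in an analysis of Week 1 only.

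Its size rests on assumed reduction rates and an assumed link to the Week 1 count. With SC0232 values and about 5 lubiprostone subjects removed, a moderate link costs about 3 to 4 points of PPS power and 0.1 SBM/week. The loss to 86%, with a mean difference of 1.4, needs every subject with at least 14 SBMs to be reduced and should be read as a near-worst case. Without a link there is essentially no effect. Under the threshold rule in both arms there is no power loss with the SC0831 or planning values.

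A reader might also infer that the trial's main conclusion is at risk. It is not: the primary van Elteren test on the FAS, its confidence interval and the sample size do not use the PPS. Where high counts on lubiprostone are the ones removed, the distortion is toward a smaller effect.

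**What to change.** In SAP 7.2, extend the criterion "Dose of randomized treatment was adjusted" with the words: before the end of Week 1 (168 hours after the first dose). Date the adjustment by the time of reduction already defined in SAP 7.8.1, and apply that definition to all reductions, whether or not recorded as due to an adverse event. Keep subjects reduced after Week 1 in the PPS and list them.

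The 168-hour cut, and not the visit, decides the matter, so reductions between visits or at an early Visit 3 are still excluded. The cost is one clause before unblinding, with no change to the primary FAS test, the sample size or data collection. If nobody is reduced after Week 1, the PPS is the same under both wordings.
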